## APPENDIX 3    QUESTIONNAIRES/ASSESSMENTS

### Appendix 3.1    Diagnostic Criteria for Clinical Diagnosis of Tuberous Sclerosis

The following diagnostic criteria were adapted from the 2012 International TSC Consensus Conference ([Northrup 2013](#)).

#### Genetic Diagnostic Criteria for *Definite* TSC

The identification of either a *TSC1* or *TSC2* pathogenic mutation in DNA from normal tissue is sufficient to make a definite diagnosis of TSC.

A pathogenic mutation is defined as a mutation that clearly inactivates the function of the *TSC1* or *TSC2* proteins (e.g., out-of-frame indel or nonsense mutation), prevents protein synthesis (e.g., large genomic deletion), or is a missense mutation whose effect on protein function has been established by functional assessment. Other *TSC1* or *TSC2* variants whose effect on function is less certain do not meet these criteria and are not sufficient to make a definite diagnosis of TSC.

**Note:** Ten percent to 25% of patients with TSC have no mutation identified by conventional genetic testing, and a normal result does not exclude TSC, or have any effect on the use of clinical diagnostic criteria to diagnose TSC.

#### Clinical Diagnostic Criteria for TSC

Major Features	Minor Features
Hypomelanotic macules ( $\geq 3$ , at least 5-mm diameter)	“Confetti” skin lesions
Angiofibromas ( $\geq 3$ ) or fibrous cephalic plaque	Dental enamel pits ( $>3$ )
Ungual fibromas ( $\geq 2$ )	Intraoral fibromas ( $\geq 2$ )
Shagreen patch	Retinal achromic patch
Multiple retinal hamartomas	Multiple renal cysts
Cortical dysplasias*	Nonrenal hamartomas
Subependymal nodules	
Subependymal giant cell astrocytoma	
Cardiac rhabdomyoma	
Lymphangioleiomyomatosis (LAM)†	
Angiomyolipomas ( $\geq 2$ )†	

\*Includes tubers and cerebral white matter radial migration lines.

[figure not shown]
†A combination of the two major clinical features (LAM and angiomyolipomas) without other features does not meet criteria for a definite diagnosis.

**Definite Diagnosis:** Two major features **or** 1 major feature with  $\geq 2$  minor features

**Possible Diagnosis:** Either 1 major feature **or**  $\geq 2$  minor features

## Appendix 3.2 International League Against Epilepsy Seizure Classification

### ILAE 2017 Classification of Seizure Types Expanded Version 

### **Appendix 3.3    Ethical Considerations for Clinical Trials on Medicinal Products Conducted with Minors**

Preterm and term neonates have very limited blood volume and, when sick, are often anaemic due to frequent routine sampling. Micro-methods on dry spots and scavenged blood remnants should be used whenever possible, since they reduce trial-related blood loss. Opportunistic, population, or sparse sampling, or other innovative methods could also reduce the frequency and volume of blood sampling. Although not evidence based, the following recommendations can be made: per individual, the research related blood loss (including any waste) as a general rule should not exceed 3% of the total blood volume over a period of four weeks, and should not exceed 1% at any single time. This recommendation leads to the allowable sample volumes, indicated in the table below. Routine health care may require significant blood sampling (recorded in infants and neonates), and the indicated research related blood volumes may even be excessive, especially in (preterm newborn) infants. This means that in individual cases, acceptable research related blood loss may be lower than indicated in the table below. Research related blood sampling and volumes should always be justified in the protocol and explained in the patient information material. Blood transfusions (or iron or erythropoietin supplementation) should not be used as a convenience to justify increased volume or frequency of blood sampling as per relevant EU guidance on ethical considerations for clinical trials on medicinal products conducted with minors.

Body weight (kg)	Circulating total blood volume (ml)	Maximum allowable sample volume over 4 weeks (ml) - 3% of total blood volume	Maximum allowable sample volume at single time (ml) - 1% of total blood volume
0.5 - 1.5	50 - 150	1.5 - 4.5	0.5 - 1.5
2.5 - 5	250 - 500	7.5 - 15	2.5 - 5
5 - 12	480 - 960	14.4 - 28.8	4.8 - 9.6
12 - 20	960 - 1600	28.8 - 48	9.6 - 16
20 - 30	1600 - 2400	48 - 72	16 - 24
30 - 70	2400 - 5600	48 - 168	24 - 56

This statistical analysis plan (SAP) describes the planned analysis and reporting for Jazz Pharmaceuticals Research UK Limited “Jazz” protocol number GWEP17005 (An Open-label, Single-arm Study to Assess the Safety, Pharmacokinetics, and Efficacy of Adjunctive Cannabidiol Oral Solution (GWP42003-P) in Participants with Tuberous Sclerosis Complex (1 month to < 2 years of age), Dravet Syndrome (1 year to < 2 years of age), or Lennox-Gastaut Syndrome (1 year to < 2 years of age) who Experience Inadequately-controlled Seizures), dated 24-Jan-2024 version 6.0. Reference materials for this SAP include the protocol and the accompanying sample data collection documents. Operational aspects related to collection and timing of planned clinical assessments are not repeated in this SAP unless relevant to the planned analysis.

The structure and content of this SAP provides sufficient detail to meet the requirements identified by the Food and Drug Administration (FDA), European Medicines Agency (EMA), and International Conference on Harmonization (ICH) of Technical Requirements for Registration of Pharmaceuticals for Human Use: Guidance on Statistical Principles in Clinical Trials¹. All work planned and reported for this SAP will follow internationally accepted guidelines, published by the American Statistical Association² and the Royal Statistical Society³, for statistical practice.

The planned analyses identified in this SAP may be included in clinical study reports (CSRs), regulatory submissions, or future manuscripts.

The SAP described hereafter is *an a priori* plan. It will be submitted to file prior to any descriptive analysis of data pertaining to the Jazz Pharmaceuticals Research UK Limited “Jazz” (formerly GW) study GWEP17005.

In view of poor recruitment and retention, and the low likelihood of meeting planned enrollment, a decision was reached to terminate the study on 28 January 2025. Following database lock, an abbreviated CSR will be produced. This abbreviated SAP describes the analyses that will be undertaken to support CSR production.

2. Study Objectives and Endpoints

2.1 Study Objectives

2.1.1 Primary Objectives

2.1.1.1 Safety: To evaluate the safety and tolerability of adjunctive GWP42003-P assessed during the 52-week treatment period.

2.1.1.2 Exposure: To investigate the exposure of GWP42003-P and its major metabolites following multiple doses of GWP42003-P.

2.1.1.3 Efficacy: To evaluate the efficacy of GWP42003-P in reducing the frequency of indication-specific countable seizures.

Primary clinical hypothesis: GWP42003-P has a positive risk/benefit outcome in the adjunctive treatment of seizures in participants with TSC, LGS, or DS.

2.1.2 Secondary Objectives

2.1.2.1 To evaluate the efficacy of GWP42003-P in reducing the frequency of total countable seizures.

2.1.2.2 To assess the retention of participants receiving GWP42003-P.

[REDACTED]

[REDACTED]

[REDACTED]

[REDACTED]

[REDACTED]

2.2 Study Endpoints

2.2.1 Primary Endpoints – Safety

The safety profile of adjunctive GWP42003-P will be assessed by measuring:

- Adverse events (AEs) (frequency, type, and severity)
- Vital signs
- Physical examination
- 12-lead electrocardiogram (ECG)
- Clinically significant changes in laboratory parameters
- Emergence of new seizure types as recorded by AE reporting
- Comprehensive neurodevelopmental assessment

2.2.2 Primary Endpoints - Exposure

- Trough, 3-hour, and 6-hour post dose plasma concentrations of GWP42003-P and its major metabolites following multiple doses of GWP42003-P.

2.2.3 Primary Endpoints – Efficacy

- Percentage change from baseline in indication-specific* countable seizures (average per 28 days) as recorded by caregivers in seizure diaries at Week 12, every 4 weeks thereafter, and during the 4-week period prior to end of treatment (EOT).

*Focal/generalized seizures – Tuberous Sclerosis Complex (TSC)

Drop seizures – Lennox–Gastaut Syndrome (LGS)

Convulsive seizures – Dravet Syndrome (DS)

2.2.4 Secondary endpoints –Efficacy

Measurements of total countable seizures (average per 28 days) as recorded by caregivers on seizure diaries at Week 12, every 4 weeks thereafter, and during the 4-week period prior to EOT will be used to determine the following endpoints:

- Number and percentage of participants considered treatment responders, defined as those with a $\geq 50\%$ reduction from baseline in total countable seizures.
- Categorical percentage change from baseline to EOT in total countable seizures as follows:
 - $> 25\%$ (increase)
 - $\geq 0\%$ to $\leq 25\%$ (increase)
 - $> -25\%$ to $< 0\%$ (reduction)
 - $> -50\%$ to $\leq -25\%$ (reduction)
 - $> -75\%$ to $\leq -50\%$ (reduction)
 - $\leq -75\%$ (reduction)
- Seizure freedom, defined as 100% reduction from baseline in total countable seizures.

2.2.5 Secondary endpoints – Retention

- Percentage of participants still taking GWP42003-P at Week 12 and every 4 weeks thereafter.

[REDACTED]

[REDACTED]

[REDACTED]

[REDACTED]

3. Overall Study Design and Plan

3.1 Overall Design

This is a Phase 3, multicentre, open-label, single-arm study that will evaluate the safety, tolerability, PK, efficacy [REDACTED] of adjunctive GWP42003-P in participants < 2 years of age with TSC, DS, or LGS. The study duration will be up to approximately 62 weeks, which includes a 4-week screening/baseline period, a 52-week dose optimization period (including a fixed 2-week titration period followed by flexible dose optimization), a 10-day taper period, and a safety follow-up period (4 weeks after the end-of-taper visit).

After signing the informed consent form (ICF), participants will be considered enrolled and will enter the screening/baseline period (Visit 1 and Visit 2 [phone visit]). Participants can be rescreened once, at the discretion of the investigator and following approval from the medical monitor. Rescreened participants will be assigned a new participant number and all screening assessments will be repeated.

At Visit 3, participants who continue to meet eligibility criteria will initiate the 52-week treatment period with the study intervention (GWP42003-P) as adjunctive therapy (i.e. in addition to their current antiseizure medication (ASM) regimen). GWP42003-P will be taken orally or with G-or NG-tube b.i.d (e.g., morning and evening) at about the same time each day, consistently with or without food. During the first 2 weeks of treatment (i.e., the fixed titration period), participants should begin titrating GWP42003-P at a rate of 5 mg/kg/week, reaching the target dose level of 10 mg/kg/day (unless the participant cannot tolerate this dose).

[figure not shown]
Starting at Visit 5, after titrating to the target dose level, investigators will have the option to titrate a participant's dose no more rapidly than 5 mg/kg every 7 days, up to a maximum dose of 20 mg/kg/day (for LGS and DS) or 25 mg/kg/day (for TSC), as recommended and based on the participant's individual response and tolerability. The investigator will determine if additional dose adjustments are warranted during scheduled or unscheduled visits throughout the remainder of the 52-week treatment period.

If a participant experiences tolerability issues related to the study intervention or an AE occurs at any time during the 52-week treatment period, the investigator may consider temporarily or

permanently reducing the current dosage, following discussion with the medical monitor. Doses may be decreased below the target dose level based on safety and tolerability. Where possible, participants should be encouraged to return to the target dose level. Investigators should regularly monitor a participant's response to treatment and re-evaluate the need for adjustments to dosage at the next study visit, if applicable.

In general, doses should not be adjusted within the 3 days prior to PK study visits, unless clinically indicated for safety. If a dose adjustment is needed during the 3 days prior to a PK study visit, the PK study visit should be rescheduled to occur > 3 days after the dose adjustment. Doses may be adjusted during PK study visits after all PK samples have been collected. The rationale for any dosage changes will be documented in the appropriate eCRF.

Figure 1 Study Schema

Participants will continue study intervention treatment until the EOT visit, after which they will initiate a taper period to titrate off the study intervention at home. The taper period will last 10 days and end with the end-of-taper visit. A safety follow-up visit (phone call or visit) will occur 4 weeks after the end-of-taper visit (i.e., 4 weeks after the last dose of the GWP42003-P).

If a participant discontinues the study intervention or study prematurely (i.e., before the EOT visit), the participant should be encouraged to complete an early termination (ET) visit as soon as possible, followed by a 10-day taper period if clinically indicated (i.e., unless the participant must discontinue treatment due to reasons related to safety and tolerability). A safety follow-up visit (phone call or visit, if needed) will occur 4 weeks after the participant's last dose of GWP42003-P.

3.2 Sample Size and Power

Up to 27 participants will be assigned to receive the study intervention in order to achieve 18 evaluable participants, which the Pediatric Investigational Plan for GWP42003-P considers sufficient to characterize PK in children < 2 years of age. Enrolment will be stratified to ensure that at least 5 participants each with LGS and DS (1 to < 2 years of age) and 8 participants with TSC (4 participants < 1 year of age and 4 participants aged 1 to < 2 years) are included in this study, in order to achieve 18 evaluable participants. There will be no formal hypothesis testing and as such no formal sample size calculation has been performed. Evaluability is defined in Section 5.0 Analysis Populations.

3.3 Study Population

Male or female participants with TSC (1 month to < 2 years of age), or DS (1 year to < 2 years of age), or LGS (1 year to < 2 years of age) within the specified age range at the time of initial informed consent may enter the study.

Participants with TSC must have a diagnosis per the 2012 International Tuberous Sclerosis Complex Consensus Conference. Participants with LGS or DS must have a diagnosis that is consistent with International League Against Epilepsy (ILAE) guidelines and confirmed by The Epilepsy Study Consortium (ESCI). VEEG shall be available for confirmation of diagnosis.

Participants to be enrolled are currently taking ≥ 1 ASMs at a dose that remains stable 2 weeks prior to Visit 3 and during the treatment period. Where required for participant safety, adjustments of concomitant ASMs or addition of new ASM may be permitted following discussion with the medical monitor.

Participants must have seizures which are not adequately controlled through their current ASMs, defined as ≥ 1 seizure reported on the seizure diary during the screening/baseline period.

The entire list of inclusion/exclusion criteria can be found in Clinical Study Protocol.

3.4 Method of Assigning Participants to Treatment Groups

Enrolment will be stratified via the Randomisation and Trial Supply Management (RTSM) to ensure that at least 5 participants each with LGS and DS (1 to < 2 years of age) and 8 participants with TSC (4 participants < 1 year of age and 4 participants aged 1 to < 2 years) are included in this study in order to achieve 18 evaluable participants. All participants will receive GWP42003-P in this nonrandomised study.

The RTSM will be used to manage study intervention supply. The RTSM system will be used at each clinic visit in order to:

- Obtain a participant's number.
- Obtain dispensing information.
- Provide completion/taper/premature termination information.

3.5 Treatments Administered

The study intervention is GWP42003-P oral solution (100 mg/mL CBD dissolved in the excipients sesame oil and anhydrous ethanol [10% v/v], with sweetener [sucralose], and strawberry flavoring).

On Day 1 of treatment with GWP42003-P, participants will begin dosing with 5 mg/kg/day GWP42003-P (2.5 mg/kg BID). On Day 8 (± 3 days), the dose will be increased to 10 mg/kg/day (5 mg/kg BID). Participants will be observed on Day 15 and, subsequently, the dose may be escalated further based on individual clinical response and tolerability; doses may increase up to a maximum of 20 mg/kg/day GWP42003-P (10 mg/kg BID) for LGS and DS, or 25 mg/kg/day GWP42003-P (12.5 mg/kg BID) for TSC. If clinically indicated for safety, participants may decrease their dose at any time. Participants discontinuing GWP42003-P treatment at the end of the study, or at any other time if they discontinue treatment early, should undergo a 10-day taper period if clinically indicated (i.e., if no safety reasons prohibit continued treatment). If a provider chooses to transfer the participant to a commercially available product above the 25mg/kg/day amount, then the participant must be terminated from the study and complete an EOT/ET visit.

3.6 Blinding and Unblinding

No blinding is applied, being an open-label study.

3.7 Schedule of Events

Visit schedule for the study is provided in the study protocol.

3.8 End of Study Definition

A participant is considered to have completed the study if they have completed all phases of the study, including the last scheduled procedure. The end of the study is defined as the date of the last visit of the last participant in the study or last contact, whichever occurs last.

4. Statistical Analysis and Reporting

By-subject listings and descriptive summaries, if any, will be performed using SAS (release 9.4 or higher) after the database is locked.

4.1 Introduction

Continuous (quantitative) variable summaries will include the number of participants (n) with non-missing values, the number of missing values, mean, standard deviation (SD), median, Q1, Q3, minimum, and maximum, unless otherwise specified.

Categorical (qualitative) variable summaries will include the frequency and percentage of patients who are in the particular category or each possible value. In general, the denominator for the percentage calculation will be based upon the total number of participants in the study population with the non-missing value of the categorical variable, unless otherwise specified.

The number of missing values will be calculated as difference of the total number of participants in the study population minus the number of non-missing values.

The minimum and maximum will be reported with the same degree of precision (i.e., the same number of decimal places) as the observed data. Measures of location (mean, median, Q1, and Q3) will be reported to 1 degree of precision more than the observed data and measures of spread (SD) will be reported to 2 degrees of precision more than the observed data.

Percentages will be presented with one decimal place, unless otherwise specified.

6.1 Statistical Definitions and Algorithms

6.1.1 Conventions for treatment/visit naming

In all tables and listings, the study visits will be referred to and labelled as per Table 1.

Table 1 Study Visits

Actual Visit	Visit Label	Phone Visit
Visit 1	Screening	
Visit 2: Baseline	Baseline	X
Visit 3: Day 1	Day 1 [§]	
Visit 4: Day 8	Day 8	X
Visit 5: Day 15	Day 15	
Visit 6: Day 22	Day 22	X
Visit 7: Day 29	Day 29	
Visit 8: Day 36	Day 36	X
Visit 9: Day 57	Day 57	
Visit 10: Day 85	Day 85	
Visit 11: Day 113	Day 113	X
Visit 12: Day 141	Day 141	X
Visit 13: Day 169	Day 169	
Visit 14: Day 197	Day 197	X
Visit 15: Day 225	Day 225	X
Visit 16: Day 253	Day 253	
Visit 17: Day 281	Day 281	X
Visit 18: Day 309	Day 309	X
Visit 19: Day 337	Day 337	X

Visit 20: Day 365	EOT/ET	
Visit 21: Day 375	End of Taper	
Visit 22: Day 403	Safety Follow-up ^f	X

[§] occurs 14 days (+ 3 days) after Visit 2, but not <28 days after Visit 1

^f Phone or clinic visit

6.1.2 Baseline

For participants who meet the eligibility criteria, the baseline is defined as follows:

For ITQOL-SF47, the baseline is based on the assessment at Visit 3.

For all safety endpoints (e.g., vital signs, physical examination, 12-lead electrocardiogram, laboratory parameters), the last non-missing observation recorded before the first study intervention administration will be used as the baseline observation for all calculations, if required.

For safety endpoints, if no observation is available before administration of the study intervention, then the first non-missing observation during the same day of study intervention administration will be used as the baseline observation.

6.1.3 Last Visit

The last visit for endpoints assessed at clinic visits is defined as the last scheduled visit (not including the end of taper or safety follow-up visits) at which a participant's last evaluation is performed.

6.1.4 Study Periods

The four study periods are the following:

- Screening/Baseline, defined as Day -28 to Day -1
- Treatment period, defined as Day 1 to Day 365
- Taper Period, defined as Day 366 to Day 375
- Safety Follow-up Period, defined as Day 376 to Day 403.

6.1.5 Day Numbering

The first day of treatment (Day 1) will be the date on the 'Enrolment Verification' eCRF, under Visit 3, RTSM Enrolment date.

Any days prior to Day 1 will be numbered relative to this day and calculated as:

Date – (Date of Day 1), to give Day -1, -2, -3 etc.

Any day post Day 1 will be calculated as:

1 + Date – (Date of Day 1), to give Day 1, 2, 3 etc.

6.1.6 Analysis Visit Windows

If applicable for summarizing or listing safety endpoints (Biochemistry, Hematology, Urinalysis, Vital Signs, ECG, Physical Examination), the following analysis visits are defined:

Table 2. Analysis Visits

Actual Visit	Visit Label	Analysis Visit	Target Study Day (AWTARGET)	Window Days	Analysis Window Study Day	
					Low (AWLO)	High (AWHI)
Visit 2: Baseline	Baseline	Baseline	-14	±3	-17	-11
Visit 3: Day 1 [§]	Day 1 [§]	Day 1	1	±3	-3	4
Visit 4: Day 8	Day 8	Week 1	8	±3	5	11
Visit 5: Day 15	Day 15	Week 2	15	±3	12	18
Visit 6: Day 22	Day 22	Week 3	22	±3	19	25
Visit 7: Day 29	Day 29	Week 4	29	±3	26	32
Visit 8: Day 36	Day 36	Week 6	36	±3	33	39
Visit 9: Day 57	Day 57	Week 8	57	±7	50	64
Visit 10: Day 85	Day 85	Week 12	85	±7	78	92
Visit 11: Day 113	Day 113	Week 16	113	±7	106	120
Visit 12: Day 141	Day 141	Week 20	141	±7	134	148
Visit 13: Day 169	Day 169	Week 24	169	±7	162	176
Visit 14: Day 197	Day 197	Week 28	197	±7	190	204
Visit 15: Day 225	Day 225	Week 32	225	±7	218	232
Visit 16: Day 253	Day 253	Week 36	253	±7	246	260
Visit 17: Day 281	Day 281	Week 40	281	±7	274	288
Visit 18: Day 309	Day 309	Week 44	309	±7	302	316
Visit 19: Day 337	Day 337	Week 48	337	±7	330	344
Visit 20: Day 365	EOT/ET	Week 52	365	±7	258	372
Visit 21: Day 375	End of Taper	End of Taper	375	±3	372	378
Visit 22: Day 403	Safety Follow-up	Safety Follow-up	403	±3	400	406

[§] occurs 14 days (+ 3 days) after Visit 2, but not <28 days after Visit 1

A visit is mapped to an analysis visit which is closest to the target day. If 2 or more assessments are equidistant from the target day for a given analysis window, the later (latest) assessment is chosen for analysis. Scheduled and early termination visits will be eligible for analysis.

Unscheduled visits will not be eligible for analysis but will be listed.

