Procedures	
Screening/Baseline Period Assessments
 
Starting at Visit 1, after completion of the ICF, the following assessments will be performed: eligibility criteria will be reviewed, along with demographics, medical history, and prior and concomitant medications. Participants will undergo full physical examinations (including height/length, body weight, and head circumference); vital signs, ECG, and VEEG will also be reviewed. Clinical laboratory samples will be collected, including chemistry, haematology, and urinalysis (when possible). Participants' seizures will be classified, and the following forms should be completed and submitted to the Epilepsy Study Consortium (ESCI): the Seizure Identification Form (SIF) (for TSC) or the Seizure Identification and Diagnostic Review Form (SIF/DRF) (for LGS and DS), along with the Epilepsy Diary Reference Sheet (EDRF) (for all participants).

	
Caregivers will be trained to use paper and ePRO seizure diaries, and diary entries will be reviewed.
 
Treatment Period Assessments
 
Participants who continue to satisfy all inclusion criteria, and none of the exclusion criteria, will receive the study intervention, which will be dispensed and collected, with compliance reviewed, at timepoints specified in the SoA (APPENDIX 1). Participants will undergo the following assessments as specified in the SoA: abbreviated physical examination (including height/length, body weight, and head circumference), neurodevelopmental assessments, CGIC/CGIS, vital signs, and ECG. Concomitant medications and AEs will be recorded, and seizure type(s), and ePRO diary entries will be reviewed. Clinical laboratory samples will be collected, including chemistry, haematology, and urinalysis (when possible). Pharmacokinetic assessments will be completed for all participants.
 
End-of-Taper Assessments:
 
The following assessments will be performed: abbreviated physical examination (including height/length, body weight, and head circumference), neurodevelopmental assessments, CGIC/CGIS, and vital signs, concomitant medications recorded, and AEs, seizure types, and ePRO diary entries will be reviewed. The study intervention will be collected, and compliance will be reviewed.
 
Safety Follow-up Assessments:
 
Concomitant medications and AEs will be recorded by a telephone call or visit.

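### SAP Table 2 misprints the Week 52 lower limit (Day 258 for Day 358), and its nearest-target rule places early terminators' end-of-taper visits in treatment weeks

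*SAP*

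**What the plan says.** SAP 6.1.6, Table 2, gives each analysis visit a target study day, a window, and a lower and upper limit (AWLO, AWHI). It applies, where applicable, to summaries or listings of laboratory data, vital signs, ECG and physical examination. Three rows matter here:

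- Week 52: "EOT/ET Week 52 365 ±7 258 372"
- Week 36, for comparison: "Visit 16: Day 253 Day 253 Week 36 253 ±7 246 260"
- Day 36: "Visit 8: Day 36 Day 36 Week 6 36 ±3 33 39"

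Below the table, the mapping rule is: "A visit is mapped to an analysis visit which is closest to the target day". For ties: "If 2 or more assessments are equidistant from the target day for a given analysis window, the later (latest) assessment is chosen for analysis". On eligibility: "Scheduled and early termination visits will be eligible for analysis". Unscheduled visits are listed but not analysed. End of Taper and Safety Follow-up have fixed targets, Days 375 and 403.

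SAP 3.1 says of the taper: "The taper period will last 10 days and end with the end-of-taper visit". A child who stops early has an ET visit and then, where clinically indicated, the same 10-day taper. The protocol synopsis lists the end-of-taper assessments as including "abbreviated physical examination (including height/length, body weight, and head circumference), neurodevelopmental assessments, CGIC/CGIS, and vital signs".

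On medications, SAP 6.1.9.2 ties concomitant use to administration in the treatment period, which SAP 6.1.4 fixes as Days 1-365. SAP 9.5.1 counts any start on or after the first dose and sets no end day.

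**The concern.** The Week 52 limits do not follow from the target and window in the same row. AWLO and AWHI are the kind of values that are typed straight into a program, so a wrong digit can pass into the derived data.

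The mapping rule raises a second question. SAP section 1 says the study was stopped for poor recruitment and retention, so early terminations are to be expected. Visit 21 is a scheduled visit and is not excluded from the nearest-target rule, yet its target assumes a full year of treatment. Measurements taken after a child has tapered off the drug could therefore be filed as on-treatment data.

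The two medication definitions matter because they decide whether a drug started after Day 365 is classified as concomitant.

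**Working it through.** **1. Limits.** Inputs: target and window in each row of Table 2, and day numbering without a Day 0 (SAP 6.1.5). Formula: AWLO = target - window; AWHI = target + window.

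- Week 36: 253 - 7 = 246 and 253 + 7 = 260, as printed.
- Week 52: 365 + 7 = 372, as printed; 365 - 7 = 358, but 258 is printed. Difference: 358 - 258 = 100 days.
- All 21 rows checked: 20 agree, and only the Week 52 lower limit fails.

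Week labels: (29 - 1)/7 = 4 and (57 - 1)/7 = 8 match the table. (36 - 1)/7 = 5, but the table prints Week 6.

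**2. What 258 would do if the limits assigned visits.** Days 258-357 are wrongly added. On 3 of them (258-260) Week 52 overlaps Week 36, and on 15 each it overlaps Weeks 40, 44 and 48: 3 + 15 + 15 + 15 = 48. The remaining 52 lie in Week 52 only. Visits 17-19 (Weeks 40-48) are phone visits in SAP Table 1, so 45 of the 48 overlap days belong to weeks with no scheduled clinic visit. The only scheduled clinic visit exposed is Visit 16 on Days 258-260, plus any ET or post-ET visit.

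**3. What 258 does under nearest target.** Nothing, because the rule uses targets only. For example, Day 258 is 5 days from 253 and 107 from 365, so it is Week 36.

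**4. End-of-taper visits after early termination.** Assume the visit falls 10 days after ET.

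- ET on Day 1 gives Day 11: 3 days from Day 8, 4 from Day 15, so Week 1.
- ET on Day 100 gives Day 110: 3 days from Day 113, so Week 16. The ET visit itself is 13 days from Day 113 and 15 from Day 85, so it is also Week 16. The post-taper visit is closer and would be the one chosen.
- ET on Day 359 gives Day 369: 4 days from 365, 6 from 375, so Week 52.
- ET on Day 360 gives Day 370: 5 and 5, tied.

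Every ET day from 1 to 359 therefore puts the end-of-taper visit in a treatment week. Of the Table 2 endpoints, the synopsis schedules vital signs and physical examination at that visit.

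**5. Late scheduled EOT visits, inside ±7.**

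- Day 371: 6 days from 365, 4 from 375, so End of Taper.
- Day 372: 7 and 3, so End of Taper.

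The taper visit 10 days later (Day 381 or 382) is 6 or 7 days from 375. The EOT visit is closer, so it would be chosen for End of Taper and Week 52 would be empty.

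**6. Could the corrected limits replace the rule?** No. Within Days 1-365 they cover Days 1-39 (39 days), eleven ±7 windows for Weeks 8-48 (11 × 15 = 165) and Days 358-365 (8): 39 + 165 + 8 = 212. That leaves 365 - 212 = 153 days in no window.

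**7. Concomitant medication.** A drug that a completer starts on Days 366-403 (403 - 366 + 1 = 38 days) is concomitant under 9.5.1. Under 6.1.9.2 with 6.1.4 it is not, and it is not prior either, because it did not start and stop before Day 1. For ET on Day 100, a drug started on Days 101-138 falls within Days 1-365 and is concomitant under both.

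**The case against.** The strongest reply is that none of this reaches a reader of the report. Nearest target is the written rule, so 258 is inert. SAP 6.1.1 labels visits in all outputs by Table 1, so a Day 110 end-of-taper visit prints as End of Taper and the Day 36 visit prints as Day 36. The safety data in SAP 9.2 and 9.3 are planned as listings, which do not depend on windows. Section 4 speaks of summaries only if there are any, and any by-visit summary would be in shells that are not part of these documents. All of this stands, and it is why the impact is low.

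A second reply is that the wide window was meant to catch ET visits. This does not stand: the row states ±7, its upper limit is exactly 365 + 7, and ET can occur well before Day 258.

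A third is that the rule and the limits are already linked, because the tie sentence mentions the analysis window. That is partly right. The link is incomplete rather than absent: the SAP does not say whether a visit outside the limits is still mapped.

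A fourth is that SAP 9.5.1 prints start and stop days, so a late-started drug is visible however it is classified. That is true, but two definitions still give two classifications.

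**Conclusion.** The Week 52 lower limit is wrong by 100 days; that is certain from the row itself. Under nearest target it moves no visit. The more substantive defect is the rule's treatment of post-treatment visits: end-of-taper visits after ET on any of Days 1-359 go to a treatment week, and scheduled EOT visits on Days 371-372 go to End of Taper. The medication definitions conflict over 38 start days, for completers only.

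What is affected is the derived analysis-visit variable, any by-visit safety summary in the shells, and prior/concomitant classification in listings. The documents give no count of ET visits or of completers, so the number of children is unknown. The 359-day result assumes a taper visit exactly 10 days after ET.

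Three stronger readings are tempting but not supported.

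- A reader might infer that visits in Weeks 36-48 are being relabelled Week 52. That needs assignment by the limits, which the SAP never states.
- A reader might infer that safety findings change. Baseline (6.1.2), treatment-emergent ALT/AST (9.2.1), exposure (6.1.9.4) and adverse event reporting (9.1) do not use Table 2, and no planned estimate or test changes.
- A reader might infer that the fixed periods in 6.1.4 distort results for early terminators generally. Apart from 6.1.9.2, no output was found that depends on them, and the two medication definitions agree in the Day 100 example.

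**What to change.** In SAP 6.1.6, Table 2, change 258 to 358 and change Week 6 (Day 36) to Week 5.

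In the text below the table:

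- Assign Visit 20 when held as the scheduled EOT visit, Visit 21 (End of Taper) and Visit 22 (Safety Follow-up) by visit identity, whatever the study day.
- Use nearest target only for on-treatment visits and ET visits.
- State that AWLO and AWHI do not decide the mapping; they can serve as in-window flags. Assignment by identity also settles Day 372, which lies in both the Week 52 and End of Taper windows even after the correction.

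Use one definition of concomitant medication in 6.1.9.2 and 9.5.1.

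The cost is two table cells, a few sentences and minor programming. No new data are needed, because actual visits are already identified in SAP Table 1.
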